#### SCHEDULE OF EVENTS

Parameter	Screening Clinic Visit 1	Baseline Clinic Visit 2	Phone Visit 1	Phone Visit 2	Phone Visit 3	Phone Visit 4	Phone Visit 5	Unscheduled Visits
	Week # 0	Week # 1-2		Week #3-4	Week #5-6		Week #7-8	
Medical History	Х							
Informed consent	Х							
Physical Examination/ Visit with MD	Х	Ŧ						Х
Vital Signs	Х							
Urine pregnancy test for females *	Х							
Laboratory testing **	Х							
Beck Depression Inventory II	Х			Х			Х	
BDI - Q9			Х			Х		
Current Medication	X	Х	Х	Х	Х	Х	Х	
EDSS	Х							
Randomization		Х						
Drug dispensing		Х						
Fatigue Severity Scale	X							
MFIS		Х		Х			Х	
Insomnia Severity Index		Х		Х			Х	
Fatigue VAS		Х		Х			Х	
Sleep diary		Х		Х			Х	
Wearable sleep monitor review		Х		Х			Х	
Step count		Х		Х			Х	
Global impression		Х		Х			Х	
Adverse Event assessment		Х	Х	Х	Х	Х	Х	Х
Study drug pill counts							Х	

Ŧ Optional, indicated for any safety issues that arise
\* As indicated by fertility status
\*\* Laboratory testing: CBC, CMP

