### 7.2 Interventions:

Study medication, to include 10-mg suvorexant and matching placebo, will be provided by Merck. The active medication will be suvorexant 10 mg every bedtime. The research pharmacist at EvergreenHealth will randomize the subject and the subject is provided active and placebo, in separate containers labeled for proper order of consumption based on study assignment. Study medication will be dispensed at randomization (Visit 2, start of Treatment Period 1) with separate pill bottles marked "Period 1, use this bottle first" and "Period 2, use this bottle after the break." An extra 6-day supply of medication will be provided for each study period to allow a window for scheduling of appointments.

Optional Drug Titration: There will be an optional titration to two pills at night (changes to suvorexant 20mg or matching placebo) after 5-7 days of each active treatment period. This will be based on a phone interview entailing answering questions about drug tolerance and whether the participant would like to escalate the dose of drug.

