research pharmacy (a separate locked room containing only research medications). The investigating physicians and research coordinator will be blinded as to treatment arm until the code is broken. The randomization code may be broken by the investigator only in a medical emergency. The reasons for such an emergency will be documented carefully. The subjects will receive 2 pill bottles, each containing identical appearing active or placebo study medication tablets, with identification known only to the research pharmacist. See Section 7.2 regarding study medication preparation and distribution.

The patient will be provided with pre-stamped and pre-addressed envelopes for return of unused study medication and study diaries at end of study.

### 10.4 Phone visit 1

Phone Visit 1 will occur 5-7 days after Clinic Visit 2 to review safety and tolerability through questioning about adverse events. BDI Q9 (suicidality risk) will be administered. Subjects with answer of 2 or 3 will be asked to discontinue study medication immediately and unscheduled visit or emergency referral will be arranged. Subjects with BDI Q9 score 0 or 1 who report no AEs on suvorexant 10 mg po QHS (or matched placebo) and who report a persistent sleep disturbance will be titrated to suvorexant 20 mg po QHS (or matched placebo) using a titration decision algorhythm. At this visit, subject will be reminded to wear sleep monitors and to start recording sleep diaries every morning.

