Study scales (ISI, MFIS, VAS-F, BDI, Global impression) will be self-administered by the participant with study staff oversight, as needed. Data from the wearable activity / sleep monitor will be collected. Completion of the 7-days sleep diary and scales (sQUAL and sFRESH) will be verified remotely. Patients will be instructed to stop taking study medication and place all unused study medication from Period 1 and Period 2 in the mailing envelope. They will be asked to include all study materials (surveys and diaries) in the envelope and to mail it as soon as possible.

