#### **Statistical Analysis**

Statistical analysis will be performed by a consulting statistician contracted with EvergreenHealth and whose services we have used on recent studies in MS. All data will remain blinded throughout the data analysis and will be un-blinded only in the event of a medical emergency.

Generally, the mean over the week prior to visit 2 (baseline) will be compared to the mean over the final week of Treatment Period 1 and the mean over the final week of Treatment Period 2 for treatment effects. This will be done by treatment arm. Level of significance will be p < 0.05. Minimum drug adherence for per-protocol criteria will be 75%. We plan to do both intention to treat and per-protocol analyses.

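### The Period 1 bottle stays with the subject to day 35 and is counted once, so Period 1 adherence cannot be separated from later use of that bottle

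*Combined protocol and SAP*

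**What the plan says.** Sections 7.2 and 10.3 of the combined protocol and SAP have the subject leave Clinic Visit 2 with two bottles, labelled by period and order of use, "each containing identical appearing active or placebo study medication tablets". Section 7.2 adds: "An extra 6-day supply of medication will be provided for each study period to allow a window for scheduling of appointments". The number of tablets per bottle is not stated.

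At Phone Visit 2 (section 10.5, day 14) the subject is told to take no study drug for a week. No count, return or sealing of the Period 1 bottle is specified. Section 10.3 supplies "pre-stamped and pre-addressed envelopes for return of unused study medication and study diaries at end of study", and section 10.8 has the subject, at Phone Visit 5, "place all unused study medication from Period 1 and Period 2 in the mailing envelope". In the Schedule of Events the row "Study drug pill counts" carries a single mark, which reads as Phone Visit 5. The table layout is partly broken in the text, but section 10.8 agrees with that reading.

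Section 13 says "Minimum drug adherence for per-protocol criteria will be 75" per cent and plans both intention-to-treat and per-protocol analyses. It gives no adherence formula and does not say whether the rule applies to each period or overall.

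No other planned record dates a dose. The seven diary items listed in section 11.3 do not include study drug. The medication reviews at Phone Visits 2 and 3 are directed at prohibited drugs and, at Phone Visit 3, also at stability of the MS regimen.

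**The concern.** A count made after day 35 shows how many tablets have left the Period 1 bottle by then. The adherence rule needs the number taken by day 14. The 21 nights between (7 of washout and 14 of Period 2) are spent by a person with insomnia holding spare tablets at home.

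Two things are at stake. First, a subject who missed too many Period 1 doses can enter the per-protocol set on the strength of tablets taken later. Second, in the suvorexant-first sequence the leftovers are active drug. If taken during washout or the placebo period, they undermine the washout and can move the placebo measurement towards the suvorexant one. The Insomnia Severity Index covers the past week (section 11.1), so use in the last week of Period 2 would bear directly on the primary endpoint. In the placebo-first sequence the leftovers are placebo, and this second problem does not arise.

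**Working it through.** **Inputs.** Treatment period 14 nights and washout 7 nights (sections 5 and 7.1); 6 extra days of supply per period (section 7.2); adherence threshold 75% (section 13); optional change from one to two tablets a night after 5-7 days (section 7.2). Assumed, because not stated: one tablet a night without titration, and a bottle of 14 + 6 = 20 tablets.

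**1. The cut-off.** 0.75 × 14 = 10.5, so 11 tablets must be gone. On a 20-tablet bottle, at most 20 − 11 = 9 may be returned.

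**2. What one count is compatible with.** True adherence = (tablets gone − tablets taken after day 14) / 14.

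| Gone at day 35 | Apparent | Taken after day 14 | Taken in period | True |
|---|---|---|---|---|
| 11 | 78.6% | 0 | 11 | 78.6% |
| 11 | 78.6% | 1 | 10 | 71.4% |
| 11 | 78.6% | 3 | 8 | 57.1% |
| 11 | 78.6% | 6 | 5 | 35.7% |
| 14 | 100% | 6 | 8 | 57.1% |

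One late tablet is enough to carry a subject over the cut-off.

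**3. What the count would show.** Full Period 1 dosing plus 1 or 6 later tablets gives 15/14 = 107% or 20/14 = 143%. Net overuse is therefore visible, unless it is put down to a period that ran long: 15 gone also fits a 15-night period taken in full. Telling these apart needs the actual period length.

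**4. Titration changes the denominator.** Two tablets a night after day 5 gives 5 + 2 × 9 = 23 assigned, with a cut-off of 0.75 × 23 = 17.25, so 18. After day 7 it gives 7 + 2 × 7 = 21, with a cut-off of 15.75, so 16. Fourteen tablets gone is then 14/23 = 61% or 14/21 = 67%, not 100%. The formula needs the titration date.

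**5. Per period or overall.** If the rule is overall, 7/14 in Period 1 and 14/14 in Period 2 give 21/28 = 75%, a pass with half of one period missed.

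**6. Spare tablets if bottles allow for titration (assumption).** Covering 20 days with titration after day 5 takes 5 + 2 × 15 = 35 tablets. A bottle of 35-40 leaves an untitrated, fully adherent subject 35 − 14 = 21 to 40 − 14 = 26, against 7 + 14 = 21 nights of washout and Period 2.

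**7. Power, for context.** With a difference of 1.75, SD 4.1 and n = 45, the standard error is 4.1/√45 = 0.611. Power is Φ(1.75/0.611 − 1.96) = 81.7% by the normal approximation and 80.0% by the noncentral t, so the plan's 81% reproduces. As an illustration only, a 10% shrinkage to 1.575 gives Φ(1.575/0.611 − 1.96) = 73%. Nothing in the documents says that shrinkage of this size would occur.

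**The case against.** A reader might infer that Period 1 adherence cannot be derived at all. The documents do not support that. The bottles are separate and labelled, so a count by bottle gives a Period 1 figure on the usual pill-count assumption that missing tablets were taken as directed. Nor does one return envelope mean mixed tablets: section 10.8 does not tell subjects to empty the bottles.

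A reader might also infer that off-period dosing cannot be detected. That too goes further than the text. The heaviest misuse is the easiest to see: an untitrated subject with a 40-tablet bottle who takes all 14 doses and then one spare tablet on each of 21 nights has 35 gone against 14 assigned, or 250%. Only late doses that offset missed ones, or that pass as an extended period, stay hidden. Subjects are also told not to dose in the washout and to use the Period 2 bottle afterwards. Each call is a chance for them to mention off-period use, although no question about it is specified.

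Other limits are fair. Six spare doses is not a minimum, because the extra supply exists for scheduling slippage and a longer period uses some of it. The rows in the table with several late tablets need missed and late doses to coincide, and the documents give no frequency for that. The 75% rule is not stated to be a Period 1 rule, and its missing definition is a separate gap. Intention-to-treat does not depend on the count.

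These points narrow the concern without removing it. An assumption that nothing was taken after day 14 is weakest where spare tablets remain at home for three more weeks, and nothing planned tests it.

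**Conclusion.** The point stands in limited form, as an inexpensive improvement. The plan yields a Period 1 adherence estimate but cannot verify it separately from later use of the same bottle. With one tablet a night, a 14-night period and leftovers kept in their own bottle, an apparent 79% is compatible with 71% after one late tablet and with 36% after six.

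The direct effect is on who enters the per-protocol set and on whether the washout can be shown to have been observed. Contamination with active drug is possible in the suvorexant-first sequence only. If it occurred undetected and the drug works, it would shrink the intention-to-treat estimate as well. How often it would occur is unknown, so no bias on the Insomnia Severity Index can be stated, and the planned sample size and power need no change on this account.

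**What to change.** - **Schedule of Events and section 10.5:** add a Period 1 pill count at Phone Visit 2. The subject reads out the remaining tablets on the call, then seals the Period 1 bottle and mails it in its own prepaid envelope before the washout. Staff count it on receipt and reconcile it with the read-out.
- **Section 10.6:** at Phone Visit 3, ask and record whether any study tablet was taken during the washout.
- **Section 10.8:** have the Period 2 tablets returned in their labelled container and counted by staff.
- **Section 13:** define adherence separately for each period as tablets used divided by tablets assigned. Use the recorded titration date, the actual period length and any extra drug dispensed at unscheduled visits (section 10.9). State whether the 75% rule applies to each period.

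The cost is one extra mailing per subject, about a minute on calls already planned, and possibly a slightly smaller per-protocol set.

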### **10.9 Unscheduled Visits**

Subjects may return to the clinic for safety evaluation or to receive additional study medication as needed. Unscheduled visits will include a review of concomitant medications and any adverse effects, and, if needed in the estimation of the study physician, physical examination in whole or in part.

# 11. Outcome Measures

All outcome measures will be based on end of treatment period compared to baseline visit.

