Physical examination will be performed, both a general medical examination including vital signs and a neurological examination. Neurological exam will include disability rating by expanded disability status scale (EDSS) (Kurtzke 1983). Laboratory testing will include complete blood count (CBC), complete metabolic panel (CMP), with calculation of the Child-Pugh score for any subjects with liver dysfunction. Pre-menopausal women without surgical sterilization will have urine human chorionic gonadotropin (hCG) measured.

The wearable activity/sleep monitor will be dispensed at this visit to all subjects who meet eligibility criteria. This will be a FitBit™ device worn by the subjects throughout the remainder of the study. The research coordinator will oversee patient education around FitBit use. The FitBit is easy for subjects to put on and requires minimal user programming to upload data. Recorded outcomes are described below (see outcome measures). Subjects will be encouraged to wear the monitor 24-hours per day. Patients will be instructed to complete a sleep diary for seven days prior to next visit (see 11. Outcome measures).

## 10.3 Baseline Clinic Visit 2

Clinic Visit 2 will occur within 7-14 days after the screening visit. In addition to screening for eligibility, medications will be reviewed again to ensure stability of the MS medication regimen and absence of any prohibited medications.

Following confirmation of eligibility, an eligible patient will complete the baseline assessments of the insomnia severity index (ISI), modified fatigue impact scale (MFIS), Fatigue visual analogue scale (VAS-F), Global impression. The following measures will be provided for the participants to take home for use at the time of Phone Visit 2 and Phone Visit 5: Study scales (ISI, MFIS, VAS-F, BDI, Global impression). Sleep diaries will be provided for use after Phone Visit 1 and Phone Visit 3.

Following confirmation of eligibility, an eligible patient will be randomized in a 1:1 randomization scheme to receive suvorexant 10 mg qhs or placebo. Randomization will occur at the research pharmacy of EvergreenHealth using a computer-generated randomization list. The pharmacist will maintain a codebook indicating the treatment allocation of each subject. Study medication will be delivered by the research pharmacist to the research study staff from the

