### • Subjective Global Impression of Change

This is a single question: "How would you rate change in your level of physical and mental function, during the study?" Response ranging from "Extremely improved", "Much improved", "Slightly improved", "No change", "Slightly worse", "Much worse", and "Extremely worse".

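### The global impression of change is also asked before any dose, and the end-versus-baseline rule that covers it does not suit an item that already asks for change

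*Combined protocol and SAP*

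**What the plan says.** Four places in the combined protocol and SAP bear on this.

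- **Definition (Section 11.2).** The only global impression defined is a single question, "How would you rate change in your level of physical and mental function, during the study", with seven answers from extreme improvement to extreme worsening and No change in the middle. It is a secondary efficacy measure.
- **Timing (Schedule of Events and Section 10.3).** The Schedule row headed "Global impression" has the same three marks as the ISI, MFIS and fatigue VAS rows: Baseline Visit 2, Phone Visit 2 and Phone Visit 5. The text of Section 10.3 agrees; its list of baseline assessments ends with "Fatigue visual analogue scale (VAS-F), Global impression". So the Visit 2 entry is not an accident of a broken table. Section 10.3 describes randomisation only after these assessments, and Section 7.2 says "Study medication will be dispensed at randomization (Visit 2, start of Treatment Period 1". The baseline answer therefore comes before any study drug.
- **Outcome rule (Section 11).** "All outcome measures will be based on end of treatment period compared to baseline visit". The global impression is not exempted.
- **Analysis (Section 13, Statistical Analysis).** "Generally, the mean over the week prior to visit 2 (baseline) will be compared to the mean over the final week of Treatment Period 1". Period 2 is treated likewise, by treatment arm. No other analysis is given for the global impression.

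**The concern.** For the ISI, MFIS or VAS-F, the baseline is a measurement of status, and end of period against baseline gives change in status. The global impression works differently: the end-of-period answer is already a statement of change. Its Visit 2 answer rates change before treatment has begun, so it is not a starting level against which the later answer can be set.

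At stake is one listed secondary outcome. If the general rule is applied to it as written, the reported by-arm result will look like a treatment effect without being one, although the crossover offers a controlled comparison of the same ratings at no extra cost.

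**Working it through.** **1. The plan's own figure.** The documents give no SD, effect size or power for the global impression. The only computed design figure is the 81% power for the ISI in Section 13: difference 1.75, SD of the difference 4.1, 45 analysed, two-sided 5%.

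Power = Φ(1.75 × √45 / 4.1 − 1.960) = Φ(2.863 − 1.960) = Φ(0.903) = 0.817.

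The noncentral t with 44 df gives 0.800. The stated figure reproduces within two points. It does not use the global impression, so nothing below touches it.

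**2. The rule applied to two kinds of item.**

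| | ISI | Global impression |
|---|---|---|
| Visit 2 answer | Insomnia severity now | Change before any dose |
| End-of-period answer | Insomnia severity now | Change during the study |
| End against baseline | Change in severity | A rating of change against another rating of change |

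**3. Algebra.** Let B be the Visit 2 rating and S and P the same subject's ratings at the end of the suvorexant and placebo periods. If the comparison is taken as a difference, the rule yields S − B and P − B.

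- If every subject answers No change at Visit 2, B is a constant c. S − B is then S − c, and testing its mean against zero tests the end rating against the scale midpoint, with no control.
- If answers at Visit 2 vary, B brings in variation that treatment cannot have caused.
- In the within-subject contrast, (S − B) − (P − B) = S − P. There is one baseline shared by both periods, so B drops out whatever its value.

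**4. Size of the added variation.** Let r be the SD of B divided by the SD of the end rating, and ρ their correlation. Then

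SD(end − B) / SD(end) = √(1 + r² − 2ρr).

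Neither r nor ρ is in the documents. Assumed values give:

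| r | ρ | Factor |
|---|---|---|
| 0 (all No change) | – | 1.00 |
| 0.5 | 0 | √1.25 = 1.12 |
| 1 | 0 | √2 = 1.41 |
| 1 | 0.5 | √1 = 1.00 |

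**5. Recall span of the later ratings.** The item asks about the study, not the period. At Phone Visit 5 (day 35) the time since baseline is 14 days of Period 1, 7 of washout and 14 of Period 2, so Period 2 is 14/35 = 40% of it. Counted from screening, 7 to 14 days earlier, it is 14/42 = 33% to 14/49 = 29%. At Phone Visit 2 the only treatment covered is Period 1. The two end-of-period answers therefore do not cover like spans, and removing the Visit 2 question alone would not make them comparable.

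**The case against.** The strongest reply is that the baseline answer may do no harm. Section 13 bases power on a crossover treatment difference, and Section 5 describes the primary outcome as change from baseline under each of the two conditions. Both passages concern the ISI, but they suggest that a suvorexant-against-placebo contrast is intended, and in its within-subject form B cancels. This stands. It confines the problem to the by-arm comparison with baseline, which is nevertheless the only comparison the plan states for this item.

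Other points also have force.

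- Section 11 speaks of comparison and gives no formula; subtraction is a literal reading of a general sentence. Section 13 is hedged by its opening word, and a mean over a week does not fit a question asked once per visit. Still, no alternative rule is offered.
- Testing each arm against its own baseline is uncontrolled for every outcome here. What is particular to this item is that its baseline is not a status value.
- Equal spread sits badly with a question most subjects would probably answer No change before treatment. That points to a small r and a factor near 1.
- Visit 2 falls 7 to 14 days after screening, so a subject has some interval to rate. It contains no treatment, and the answer is still not a status value.
- A separate severity rating may have been meant at Visit 2. None is defined, so the text would need correcting in that case too.

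**Conclusion.** The point holds as a minor one. A change item is scheduled before any dose, the end-versus-baseline rule covers it without exception, and the resulting by-arm comparison does not validly measure treatment effect for this secondary outcome.

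A reader might infer that the outcome is meaningless altogether. The documents do not support that: the shared baseline cancels in a direct suvorexant-minus-placebo contrast, which the design permits. Nor do they support saying that the SD will rise by 41%. The factor of 1.41 needs independence and equal spread, is an upper illustration rather than an estimate, and no SD for the item is given; the true inflation may be negligible. The primary ISI analysis and its stated power are unaffected.

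**What to change.** 1. Remove the global impression from the Visit 2 column of the Schedule of Events and from the baseline assessments in Section 10.3. Keep the take-home copies for Phone Visits 2 and 5. If a status rating was intended at Visit 2, define it as a separate item.
2. Add to the Section 11 sentence: *except the global impression of change, for which the end-of-period ratings under suvorexant and placebo are compared directly within subject*. An ordinal or signed-rank method would suit the seven ordered categories.
3. Reword the item in Section 11.2 to ask about change since the start of the current treatment period, so that the two ratings are comparable.

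The cost is two deletions, one clause and one reworded question, with one question fewer at Visit 2. No visit, measurement or sample size changes. If ratings have already been collected, the clause in step 2 still applies, but the recall span of answers already given cannot be repaired and should be stated as a limitation.
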